The HbA1C outcome was used for the sample size calculation. Since we are collecting HbA1C every 8 weeks, we are able to leverage the repeated measures design in the estimation of the sample size needed for this study. This allows us to gain efficiency and reduce the number of subjects needed. Thus, for an effect size 'f' of 0.14, which is between small (0.10) and medium (0.25), an alpha of 0.05 and power of 0.80, we need a total of 92 study subjects. Allowing for some attrition in study subjects, we are planning to enroll 100 patients.

Note that this type of sample estimation requires that we specify the variance across observations (sphericity) and the correlation across observations. We specified both at 0.60. We calculated sample size using G*Power.

Data Analysis Plan

The data analysis will start with completion of the **CONSORT** diagram, with an analysis of differences between those who completed the study and those who did not (t-tests and chi-square tests, as needed, comparing basic demographics and baseline health characteristics), so that the researchers in this area can understand the extent to which our study contains bias.

Next, we will calculate summary statistics (means, medians, proportions, etc.) of all baseline measurements, overall and by study arm, so that we can fully characterize the study cohort.

Using the CGM data, we will graph each participant's trajectories over time and review each, examining for major patterns in the trajectories. Note that typically statistical analyses emphasize homogeneity in the data; however, this approach will allow for understanding of heterogeneity. As part of this examination of the CGM data, the analysis will calculate each participant's measures of glycemic variability (such as mean amplitude of glycemic excursions, coefficient of variation, etc.), HbA1C values, and fructosamine values and overlay them on each graph. This part of the analysis is predominantly exploratory.

For the statistical, hypothesis-testing examinations of HbA1C, fructosamine, CGM readings, and glycemic variability across key time points, we will conduct mixed models (i.e., multilevel model) analyses, which will allow us to quantify within-between interactions, or changes within subjects over time and differences across groups. These models can also include multiple independent variables/covariates.

F. Inclusion/Exclusion Criteria

Inclusion criteria:

1. Pregnancy and Gestation \leq 30 weeks
2. Singleton pregnancy

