3. Confirmed GDM (by 75g or 100g oral glucose tolerance test or HbA1c)
4. Able to read English
5. Is able to read, understand, and sign the Informed Consent Form (ICF) and if applicable, an Authorization to Use and Disclose Protected Health Information form (consistent with Health Insurance Portability and Accountability Act of 1996 [HIPAA] legislation), communicate with the investigator, and understand and comply with protocol requirements

Exclusion criteria:

1. Pre-gestational Type 1 or Type 2 diabetes.
2. Newly diagnosed overt-diabetes in pregnancy [HbA1c \geq 48 mmol/mol (6.5%), fasting glucose \geq 7.0 mmol/l, random glucose \geq 11.1 mmol/l].
3. Pregnancies with established fetal anomalies (aside from echogenic intracardiac foci and/or renal pyelectasis) or possible preterm delivery secondary to maternal disease besides GDM
4. Known endogenous/exogenous Cushing's syndrome
5. Known chronic infections
6. Current use of any oral form of steroid medication
7. Already receiving continuous glucose monitoring (CGM)
8. History of bariatric surgery
9. Gestational Age less than 14 weeks

G. Diagnosis of GDM:

Per UW protocol and based upon the ACOG Practice Bulletin on gestational diabetes early screening for GDM prior to 20 weeks is recommended, preferentially in the first trimester in those at high risk especially in the overweight or obese (BMI ≥ 25 or ≥ 23 for Asian)

Screening Strategy for Detecting Pregestational Diabetes or Early Gestational Diabetes Mellitus (consider testing in all overweight/obese women (i.e. BMI ≥ 25 or ≥ 23 for Asian Americans) with one of more of the following risk factors:

Physical inactivity

First-degree relative with diabetes

High-risk race or ethnicity (African American, Latino, Native American, Asian Americans, Pacific Islander)

Prior infant weighing ≥ 4000 g (~9lbs)

Previous GDM

Hypertension (140/90 mmHg or on therapy for hypertension)

High-density lipoprotein cholesterol level <35 mg/dL (0.90 mmol/L),

Triglyceride level >250 mg/dL (2.82 mmol/L)

Polycystic ovarian syndrome

Hemoglobin A1C $\geq 5.7\%$, impaired glucose tolerance, or impaired fasting glucose on previous testing

Other clinical conditions associated with insulin resistance (ex: pre-pregnancy BMI ≥ 40 , acanthosis nigricans)

History of cardiovascular disease

Early Screening & Diagnosis of GDM:

Screening may include early HbA1C in the above higher risk population. Per UW protocol interpretation of HbA1C will be:

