Study Design: Interested volunteers will be screened by telephone or in person in respective clinics or via televisit and then scheduled for a screening visit (week 0). If potential participants express interest, they will be provided an email address or phone number to call for more information. Alternatively, participants will be asked if they would like to be called to receive more information and are willing to provide their contact information to study staff. If after receiving more information, the potential participant is interested, then pre-screening questions (appendix D) will be asked. If still eligible, then a screening appointment will be arranged by study staff. If the participant is not interested in participating the participant will continue standard OB care for gestational diabetes.

Study visits and intervention: Upon arriving to the pre-intervention visit, informed consent will be obtained after which a point of care HbA1c (if no HbA1c available within the last 2 weeks) will be obtained and oral glucose tolerance test (OGTT) and or HbA1c results reviewed and inclusion/exclusion criteria reviewed. At the pre-intervention session (week 0) the control group will wear CGM for 10 days blinded. The intervention group will be given CGM training and instructions and start Real Time-CGM (RT-CGM). Controls will be asked to follow their OB provider's instructions for checking blood sugar via capillary blood glucose (ie fingersticks). If no recommendations have been given, instructions will be to start checking fingersticks fasting and 1-hour post-meals, which is typical for GDM management. All participants will be asked to write their glucose levels/results in a log provided. RT-CGM participants will be asked to review their RT-CGM and write down their fasting glucose in am, prior to each meal and 1 and 2 hours post-meal. As well they will be instructed to document any sugars < 60 mg/dl seen by CGM in their log.

Participants will then follow-up at week 2 (session 2) at which time the control group will have their blinded CGM data collected and the RT-CGM group will download their CGM data and ensure CGM working appropriately. The control group will continue to monitor fingerstick blood glucose as recommended by their

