Vital signs will be collected, including height, weight (current and pre-pregnancy), blood pressure, maternal resting heart rate, and estimated gestational age. Maternal ultrasound results will be reviewed if available.

Glucose tolerance test results will be reviewed. Two blood pressure and pulse readings will be taken and HbA1c, both point of care (fingerstick) and HbA1c serum and fructosamine via LabCorp will be obtained. Approximately 1 teaspoon of blood will be drawn. If a patient has an HbA1c documented in the medical record within 2 weeks of the pre-intervention session, then the point of care HbA1c will not be done. The available HbA1c will be used. If they meet all inclusion and exclusion criteria (as outlined above), they will be randomized into either the RT-CGM intervention or control arm at the screening visit.

At the pre-intervention session (week 0) the control GDM group will be asked to wear the CGM blinded for 10 days. They will be asked to continue their usual diet and activity. If, for any reason, the CGM device fails to capture at least 3 days worth of data, the subject may be asked to repeat this measurement at an unscheduled visit. The control group will be given a glucose meter (onetouch) and instructed to follow their obstetric provider's recommendations about checking glucose by meter or if they have not been given instructions or do not remember their instructions they will be asked to check sugars fasting and 1 hour after meals. They will also be given a handout that explains glucose goals and how food and activity effects glucose levels. (Appendix A1,A2). The intervention group will be given RT-CGM and instructed on use with a handout that explains glucose goals and how food and activity effects glucose levels (see handout/Appendix A). The intervention group will also be given a glucose meter (onetouch) and instructed to use for symptoms of low glucose or if they question the accuracy of the CGM. Both groups will be given standard gestational diabetes teaching and nutrition counseling by the RN in clinic and with individual nutrition appointments with the nutritionist, as per current local standard of care.

Participants will be given self-report questionnaires on physical activity, nutrition, sleep history, pregnancy history and overall wellness. Week 0 consenting and baseline data/measurements will take between 1 hour 30 minutes and 2 hours.

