Week 2 (Visit 1a): Gestational Age 14-16 (Early GDM Dx) or 24-28 weeks (Regular GDM Dx)

RT-CGM and meter will be downloaded for intervention group and meter downloaded for the control group. Glucose logs will be collected. All participants will confirm they have completed RN gestational DM education and nutrition appointments per local standard of care. Vital signs, weight and medications and dose will be recorded at each visit and maternal ultrasound results if available (appendix M).

Week 6 (Visit 1b): Gestational Age 20-22 weeks (Early GDM Dx)

RT-CGM and meter will be downloaded for the intervention group and meter downloaded for the control group. Vital signs, weight and medications and dose will be recorded at each visit and maternal ultrasound results if available (appendix M).

Week 6/Week 14 (Visit 2): Gestational Age 30-32 weeks (Both Early GDM Dx and Regular GDM Dx)

RT-CGM and meter will be downloaded for the intervention group and meter downloaded for the control group. Vital signs, weight and medications and dose will be recorded at each visit and maternal ultrasound results if available (appendix M).

The control group will wear blinded CGM for 10 days and return during regularly scheduled OB visit. The study staff will follow up with participants to remind them to return the devices. If for any reason, the CGM device fails to capture at least 3 days of data, the participants may be asked to repeat this measurement at an unscheduled visit.

Week 10/Week 18 (Visit 3): Gestational Age 34-36 weeks (Both Early GDM Dx and Regular GDM Dx)

RT-CGM and meter will be downloaded for the intervention group and meter downloaded for the control group. Vital signs, weight and medications and dose will be recorded at each visit and maternal ultrasound results if available (appendix M).

Questionnaire on nutrition and exercise in pregnancy and satisfaction with CGM and lifestyle changes with CGM.

The control group will wear blinded CGM for 10 days and return during regularly scheduled OB visit. HgA1c and fructosamine will be collected.

The study staff will follow up with participants to remind them to return the devices. If for any reason, the CGM device fails to capture at least 3 days of data, the participants may be asked to repeat this measurement at an unscheduled visit.

Week 14 /Week 22 (Visit 4) Gestational Age 38- 40 weeks (Both Early GDM Dx and Regular GDM Dx)

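### The mixed model leaves baseline HbA1c and the randomisation strata optional. Committing to both is a wording change that can only help precision, and at the plan's own correlation baseline adjustment lifts 80% power to about 88% if SDs are equal.

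*Combined protocol and SAP*

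**What the plan says.** Section E (Data Analysis Plan) tests HbA1c, fructosamine, CGM readings and glycaemic variability with mixed models, "which will allow us to quantify within-between interactions, or changes within subjects over time and differences across groups". On covariates it says only: "These models can also include multiple independent variables/covariates". None is named, and the text does not say whether baseline HbA1c is one of the repeated outcomes or a covariate.

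Section E (Sample Size Estimation) sizes the trial on HbA1c: effect size f 0.14, alpha 0.05, power 0.80, 92 participants in total. Of the sphericity value and the correlation it says: "We specified both at 0.60".

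Section I randomises by permuted blocks in four strata, formed from gestational age and pre-pregnancy BMI. No section carries these factors into the analysis.

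The data exist. Section H obtains HbA1c at the screening visit, and if eligible, "they will be randomized into either the RT-CGM intervention or control arm at the screening visit". For 34-36 weeks, the Visit 3 entry says "HgA1c and fructosamine will be collected". Section K adds HbA1c at 30-32 weeks, but the entry headed "Week 6/Week 14 (Visit 2): Gestational Age 30-32 weeks" lists no draw. Sections E and H also speak of HbA1c every 8 weeks.

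**The concern.** HbA1c is measured at the visit where participants are randomised, so the two arms share one baseline mean in expectation. A group-by-time test that estimates a separate baseline mean in each arm does not use this. It amounts to an unadjusted comparison of change, and it pays for the noise in the baseline difference. Adjusting for baseline removes that cost with data already in hand.

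Two smaller things are also at stake. Covariates that are permitted but not named leave the choice open until the data are seen. And when randomisation is stratified but the model omits the strata, the standard errors do not match the design: if the strata predict HbA1c, the test is slightly conservative.

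**Working it through.** **1. Reproduce the plan's figure.** Within-between interaction F test as in G*Power, with 2 groups, N = 92, ρ = ε = 0.60 (Section E) and m = 3 measurements (Section K; Section E does not state the number used).

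- λ = f²·N·m·ε/(1−ρ), df1 = (m−1)ε = 1.2, df2 = (N−2)(m−1)ε = 108.
- f = 0.14: λ = 0.0196 × 92 × 3 × 0.6/0.4 = 8.11, power 78.4%.
- f = 0.143: λ = 8.47, power 80.1%.

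So 92 is recovered if the printed 0.14 is a rounded 0.143. With m = 4 the same formula needs 81, and with m = 5 it needs 71. The stated N therefore fits three measurements with baseline as an unconstrained outcome.

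**2. Single contrast at 34-36 weeks.** Let s be the follow-up SD divided by the baseline SD (not in the documents; range assumed). In units of baseline variance:

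- change: 1 + s² − 2ρs
- baseline-adjusted: s²(1−ρ²)
- change minus adjusted: (1−ρs)², which is never negative.

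Apart from one degree of freedom, adjustment therefore cannot lose precision. Starting from 80% for change (noncentrality 2.8016), adjusted power is Φ(2.8016/√ratio − 1.96). Noncentral t at N = 92 agrees.

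| ρ | s | variance ratio | adjusted power |
|---|---|---|---|
| 0.60 | 0.8 | 0.4096/0.68 = 0.602 | 95% |
| 0.60 | 1.0 | 0.64/0.80 = 0.800 | 88% |
| 0.60 | 1.1 | 0.7744/0.89 = 0.870 | 85% |
| 0.60 | 1.25 | 1.00/1.0625 = 0.941 | 82% |
| 0.60 | 1.5 | 1.44/1.45 = 0.993 | 80% |
| 0.40 | 1.0 | 0.84/1.20 = 0.700 | 92% |
| 0.80 | 1.0 | 0.36/0.40 = 0.900 | 84% |

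The gain vanishes at s = 1/0.60 = 1.67. Starting from 78.4% instead, ρ = 0.60 with s = 1 gives 86.6%.

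**3. Effect of the entry cut.** Section F excludes "Newly diagnosed overt-diabetes in pregnancy", including HbA1c at or above 6.5%, which trims baseline variance. If the cut lies c SD above an untruncated normal mean (assumption), the remaining baseline variance is v = 1 − ch − h², with h = φ(c)/Φ(c). The variance ratio is 0.64/(0.64 + 0.16v). For c = 1, 1.5 and 2 this gives 0.864, 0.838 and 0.819, and power 85, 86 and 87%.

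**4. Two follow-up visits, joint 2-df test, starting from 80% for change.** Effect patterns are late / linear / constant. Compound symmetry implies sphericity 1, not 0.60, so covariances with mean correlation and sphericity both 0.60 were also tried.

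| Covariance | common baseline mean | one baseline slope for both visits |
|---|---|---|
| compound symmetry, ρ = 0.60 | 84 / 89 / 91% | same |
| equal SD, r01 = r12 = 0.763, r02 = 0.273 | 97 / 96 / 80% | 82 / 78 / 80% |
| all r = 0.60, SD 1/1/2.95 | 88 / 83 / 87% | 79 / 81 / 87% |

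Across the four such covariances tried, the common-baseline-mean form gives 80-97%. A single baseline slope is not equivalent to it and can fall just below the starting 80%.

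**5. Strata.** Noncentrality after baseline adjustment at s = 1 is 2.8016/√0.8 = 3.132. If the strata explain a further share R² of residual variance (assumption), power without them is Φ(1.172/√(1−R²)) and with them Φ(3.132/√(1−R²) − 1.96). For R² of 2, 5 and 10%, power moves from 88.2, 88.5 and 89.2% to 88.6, 89.5 and 91.0%. In simulation (8,000 runs, blocks of 4, assumed strata sizes 30/30/16/16) the false-positive rate with baseline and strata in the model was 0.048-0.054.

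**The case against.** The plan allows covariates, so an analyst may adjust for baseline anyway, and then no power is lost. The comparator is inferred from the sample size. The plan's 80% belongs to a repeated-measures interaction test, not to a single 34-36 week contrast, and the printed f gives 78.4%. The gain depends on an SD ratio the documents do not give, and some of the covariances in step 4 are arithmetical illustrations rather than likely patterns for HbA1c. The protocol calls the study a pilot. All of this stands. It limits the size of the point, but the model remains unspecified and the direction of the gain is not in doubt.

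Three stronger readings are tempting and not supported:

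- *The trial is underpowered or the test invalid.* The stated N is recovered with unrounded f, and leaving baseline as an outcome is valid. Omitting the strata makes the test slightly conservative, not liberal.
- *Any form of baseline adjustment will do.* With two follow-up visits a single baseline slope can forfeit the gain (step 4).
- *CGM metrics have no untreated baseline in the intervention arm.* Section H starts real-time CGM at week 0, which suggests this. But Section J mentions a blinded portion when describing that arm's alert handout, and Section N lists real-time CGM data at baseline. The documents do not settle it.

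**Conclusion.** The point holds as one of precision and pre-specification. At the plan's correlation of 0.60, baseline adjustment of a single 34-36 week contrast turns 80% power into about 88% with equal SDs and 80-85% with a follow-up SD 1.1 to 1.5 times baseline. It gives more if the follow-up SD or the correlation is lower. These figures rest on an assumed SD ratio and on reading the planned test as an unadjusted comparison of change. The strata are worth 0.4 to 1.8 points, wholly under assumed R²; the better reason to name them is agreement with the randomisation. Nothing here shows bias, false-positive inflation or a shortfall from the planned 80%. The change is worth making because it is cheap; confidence in the size of the gain is moderate.

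**What to change.** Settle four things first:

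1. Which HbA1c is the baseline. Section H allows a point-of-care value, a laboratory value, and a chart value up to 2 weeks old. State also that it is drawn before real-time CGM can take effect; the timing of blood draws for televisits is not given. This matters most for fructosamine, which Section L describes as a 2-week average.
2. The HbA1c schedule: every 8 weeks (Sections E and H), or baseline, 30-32 and 34-36 weeks (Section K), with no draw listed at Visit 2 (Section H). This fixes the number of follow-up visits.
3. The gestational-age factor in Section I, described once as 14-24 weeks or 28 weeks and then listed as 14-24 weeks or over 24 weeks, so that model terms match the randomisation lists.
4. Whether the intervention arm has any untreated CGM baseline (Sections H, J and N).

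Then replace the covariate sentence in Section E with a stated model:

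- **HbA1c:** categorical visit, arm by post-baseline visit, a common baseline mean and unstructured covariance; or baseline HbA1c as a covariate with a baseline-by-visit interaction. Baseline should not be both outcome and covariate. Include both stratification factors, with stratum-by-visit terms if baseline is kept as an outcome.
- **Fructosamine:** the same model with one follow-up visit.
- **CGM metrics:** the strata factors, with a CGM baseline only if item 4 confirms one.

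The cost is analysis-plan wording and a few degrees of freedom. No new data are needed.

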Perception/Satisfaction with CGM and Fingersticks/Meter (Appendices J): The Harvard Joslin Diabetes Center has developed a series of questionnaires on CGM experiences, opinions and expectations that will be given at the end of the intervention and has been adapted for the GDM. Additionally, questions about food changes and activity changes that was created for CGM use(19,20) . Questionnaires have been adapted for use in those using only meter fingersticks and for GDM.

Sleep Questionnaire (appendix Q) The Pittsburgh Sleep Questionnaire is good tool for screening sleep disorders in the population and has been used in pregnancy (22,23)

N: Glucose/CGM Data /Evaluation Measures: The compliance and duration wear for participants with CGM will also be recorded. Glucose dynamics, e.g., average glucose, standard deviation, mean amplitude of glucose excursion (MAGE), time in range % (65 and 140 mg/dL), % high (>140 mg/dL), % low (<64 mg/dL), and severe low % (<54mg/dL) and coefficient of variation (CV) and other statistical measures of glucose variability in those with CGM will be reviewed from the RT- CGM device data at baseline and visit 2-4. Blinded CGM values will be obtained at baseline and visit 2 and 3.

Glucose meter: Compliance with fingersticks 4 times a day will be recorded by average number of fingersticks per day. Glucose data including: average glucose, standard deviation, mean amplitude of glucose excursion (MAGE), time in range % (65 and 140 mg/dL), % high (>140 mg/dL), % low (<64mg/dL), and severe low % (<54mg/dL) will also be recorded.

N:Antenatal Ultrasound Markers: estimated fetal weight (in grams and percentile) using Hadlock scale, Biparietal Diameter, Head circumference, abdominal circumference, and femur length. Amniotic Fluid Index.

O: Delivery Outcomes:

Obstetric Outcomes:

- 1.Gestational age at delivery
- 2.Labor status (spontaneous labor, induced labor, no labor). For induced labor include indication for induction
- 3.Mode of delivery (vaginal delivery, cesarean delivery, operative vaginal delivery) including indication for delivery
- 4.Shoulder dystocia: defined as a delivery that requires additional obstetric maneuvers to release the shoulders after gentle downward traction has failed. SD occurs when either the anterior or, less commonly, the posterior fetal shoulder impacts on the maternal symphysis or sacral promontory

Maternal Outcome:

1. Preeclampsia or GHTN
2. Maternal insulin or medication use

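### The CGM record labelled baseline is already on RT-CGM in the intervention arm, so an interaction referenced to week 0 misses any effect present in the first 10 days

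*Combined protocol and SAP*

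**What the plan says.** All references are to the combined protocol and SAP.

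- **Timing of allocation** (Section H, Screening/Pre-Intervention Visit): eligible participants are allocated at week 0: "they will be randomized into either the RT-CGM intervention or control arm at the screening visit".
- **Week-0 monitoring** (Section H, Study visits and intervention): controls wear a blinded sensor for 10 days. For the other arm: "The intervention group will be given CGM training and instructions and start Real Time-CGM (RT-CGM".
- **What else differs in that window** (Section H): of the controls, the plan says "They will be asked to continue their usual diet and activity". The intervention arm sees live readings and writes CGM values in a log; "they will be instructed to document any sugars < 60 mg/dl seen by CGM in their log". Section J sets a high alert at 140 mg/dL for that arm.
- **What does not differ** (Section H): of the controls, "They will also be given a handout that explains glucose goals and how food and activity effects glucose levels". The intervention arm gets a corresponding handout, and both arms get the standard GDM teaching and nutrition counselling.
- **The label** (Section N, Glucose/CGM Data): intervention-arm metrics come "from the RT- CGM device data at baseline and visit 2-4". For controls, "Blinded CGM values will be obtained at baseline and visit 2 and 3".
- **The analysis** (Section E, Data Analysis Plan): CGM readings and glycemic variability are tested with mixed models, "which will allow us to quantify within-between interactions, or changes within subjects over time and differences across groups". The section neither lists its key time points nor says which record is the reference.

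**The concern.** A baseline is useful as a reference because treatment cannot have affected it. Here one word covers an on-treatment record in one arm and an off-treatment record in the other. Mean glucose, time in, above and below range, MAGE, SD and CV are the Aim 1 outcomes, and all of them come from these records.

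If participants respond quickly to seeing their glucose, part of the benefit is already in the intervention arm's starting value. A change measured from that value subtracts the early benefit. A prompt and lasting effect could then be reported as no group-by-time interaction, and an on-treatment value could appear in the baseline table as if it described the participants before treatment.

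**Working it through.** **Planning figure.** The plan gives no SD, effect size or power target for any CGM metric, so there is no figure to reproduce on this point. The total of 92 was sized on HbA1c and does not enter. What can be calculated is the share of the effect that each model term estimates, and that share needs no SD.

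**Inputs**
- Records common to both arms: week 0, visit 2 (30-32 weeks) and visit 3 (34-36 weeks), from Section N. Visit 4 CGM data exist for the intervention arm only.
- d: the arm difference at visits 2 and 3, assumed equal at both.
- phi: the share of d already present in the first 10 days. This is an assumption; the documents give no value, so the range 0 to 1 is shown.
- The arm differences at the three records are therefore phi·d, d and d.

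**Formulas**
- Interaction referenced to week 0: (d + d)/2 − phi·d = (1 − phi)·d.
- Group term averaged with equal weight over the three records: (phi·d + d + d)/3 = (2 + phi)/3·d.
- Arm difference at visits 2 and 3 only: (d + d)/2 = d.

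**Share of d estimated**

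| phi | Interaction vs week 0 | Group term, three records | Visits 2-3 only |
|---|---|---|---|
| 0 | 100% | 67% | 100% |
| 0.25 | 75% | 75% | 100% |
| 0.5 | 50% | 83% | 100% |
| 0.75 | 25% | 92% | 100% |
| 1 | 0% | 100% | 100% |

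The two planned terms move in opposite directions. Early action shrinks the interaction; an effect that has not yet appeared shrinks the averaged group term. For any phi strictly between 0 and 1, both fall short of d. Only the visit 2-3 difference estimates d at every phi.

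**Week 0 as a covariate.** The same problem arises. If the within-arm slope on the week-0 value is b, the adjusted difference is d − b·phi·d = (1 − b·phi)·d, which is below d whenever b and phi are both positive.

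**Laboratory baselines.** Section H lists the HbA1c and fructosamine draw before randomisation at the screening visit, so a value drawn before the first sensor is free of RT-CGM in both arms.

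**The case against.** The strongest objection is that the faulted analysis is inferred. Section E names no reference record, the label in Section N describes data collection, and a mixed model with visit as a category can already yield the visit 2 and visit 3 arm differences. This stands in part: the plan does not state that week 0 is the reference. But the label makes it the natural one, and nothing in Section E rules it out. The (2 + phi)/3 share also rests on three equally weighted records and equal effects at visits 2 and 3.

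A reader might also infer any of the following, which the documents do not support:

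- *Early action dilutes both terms.* It does not: the group term's share rises from 67% to 100% as phi goes from 0 to 1.
- *Only the intervention arm is counselled in this window.* The handout and the GDM teaching go to both arms.
- *The trial loses a known amount of power on CGM metrics.* Any such figure depends on an SD and an effect size that the plan does not give, so none is offered.
- *The sample size, or the HbA1c and fructosamine baselines, are compromised.* The 92 concerns HbA1c, and the in-person sequence puts the blood draw ahead of randomisation. Only the televisit route, with mailed sensors, leaves the draw time open.
- *The intervention arm has a blinded run-in.* Section J mentions a blinded portion in connection with that arm's alert handout. Section H schedules no blinded wear for it, and Section J says elsewhere that blinded mode gives no alerts.

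**Conclusion.** The point holds for the Aim 1 CGM metrics. Their labelled baseline is post-randomisation in both arms and on treatment in one. If week 0 is the reference, the interaction recovers (1 − phi) of the later effect, anywhere from all of it to none. A group term averaged over the three common records recovers between two thirds and all of it.

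The timing and the label are plain in the text. The dilution depends on three things that are not: week 0 being used as the reference (inferred from the label), the value of phi, and equal effects at visits 2 and 3. It is worth fixing before any CGM data are analysed by arm.

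**What to change.** **Changes to Sections E and N**
1. Stop calling the week-0 CGM record baseline. Treat it as post-randomisation data, and use it neither as the reference nor as a covariate.
2. Name the between-arm difference at 30-32 and 34-36 weeks (visits 2 and 3), from the mixed model, as the test for CGM metrics.
3. Adjust it for the randomisation strata and for week-0 HbA1c and fructosamine drawn before the first sensor insertion. Keep participants who lack such a value, with the same missing-covariate handling in both arms.
4. Report the week-0 arm difference separately as an early effect.
5. Reconcile the mention of a blinded portion for the intervention group in Section J with Section H and with the description of blinded mode in Section J.

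**Cost.** No new visits, devices or participants are needed. Beyond wording, the draw time must be recorded against the first sensor insertion, mainly for televisit starts.

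The real downside is that no same-metric baseline remains. If phi is near 0, some precision may be lost against a change-from-week-0 contrast, by an amount that depends on correlations the plan does not give for CGM metrics. As an illustration, take equal correlations r and unit SD. The per-person variance is 1.5(1 − r) for the change and (1 + r)/2 for the visit 2-3 mean. At r = 0.5 both are 0.75, so nothing is lost. At r = 0.60, the value Section E used for HbA1c, they are 0.60 and 0.80, so the standard error rises by a factor of √(0.80/0.60) = 1.15. Even then, the change contrast has the better ratio of signal to standard error only if phi is below 1 − √(0.60/0.80) = 0.13. Equal correlations imply a sphericity of 1, not the plan's 0.60, so this shows direction only. How much precision the laboratory covariates would recover is unknown.
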